## BACKGROUND AND STUDY DESIGN/INTERVENTION

The prevalence of urolithiasis is greater than 8% and increasing in the United States (US) [1]. There are several treatment options, including ureteroscopy (with or without laser lithotripsy), extracorporeal shock wave lithotripsy, and percutaneous nephrolithotomy. A recent study in California demonstrated that ureteroscopic treatment was employed in more than 40% of interventions [2], with some nationwide estimates up to 59% [3]. At least 300,000 stone interventions are performed yearly in the US on working age adults [4], thereby, there are at least 120,000 ureteroscopies. There are several other indications for ureteroscopy, including diagnosis of structural anomaly and diagnosis and management of ureteral and renal pelvic tumors.

Depending on the specifics of the procedure, it may be advisable to place a ureteral stent intraoperatively [5]. The most commonly used variety of stent is the double J stent [6], which has long been known to cause post-operative pain in around 80% of patients, as well as irritative symptoms in a sizeable portion [7, 8]. Approximately 12% of those undergoing ureteroscopy will have an emergency department (ED) visit in the first 30 post-operative days [9], typically for stent related symptoms or post procedural pain [10]. Aside from the short-term repercussions of ureteroscopy with stent placement (such as ED visits), there are long-term issues related to pain or the treatment thereof. Recent evidence suggests that approximately 6% of opioid naïve patients who undergo ureteroscopy will become new persistent opioid users [11].

Alpha-blockers decrease ureteral stent discomfort when compared to placebo [12, 13]. Anti-muscarinic medications have also been shown to be helpful with stent related discomfort independently, or in addition to alpha blockade [14], though the evidence is mixed [15]. A recent systematic review failed to find any studies of other medications for stent related discomfort that met inclusion criteria [16]. Subsequently, a well-designed study demonstrated the utility of mirabegron for indwelling stent symptoms [17].

We learned a great deal from this pilot study. First, we saw that it was feasible to enroll patients at a relatively high rate. We approached 12 eligible patients to enroll 10. A surprisingly high number (approximately 1/3) of patients undergoing eligible procedures were not eligible for enrollment, typically due to chronic kidney disease or chronic opioid use. We were successfully able to administer the study medication and track outcomes. The number of surveys were quite burdensome – to participants, nurses, and study staff. Insurance companies regularly required prior authorization for the recommended discharge medications (but would approve relatively similar medications). We have modified the design of this study in several ways due to the lessons learned in the pilot study.

## **CRITERIA FOR SUBJECT ELIGIBILITY**

#### Subject Population

Undergoing elective ureteroscopy with stent placement at University of Missouri Hospital and affiliated facilities

#### Subject Inclusion

- Age  $\geq$  18 years
- Undergoing ureteroscopy with plan for stent placement

Subject Exclusion

- Renal insufficiency (eGFR < 50 mL/minute/1.73 m^2)
- Ureteral stent in place >30 days
- Chronic opioid use
- History of opioid abuse

- Chronic gabapentinoid use
- History of gabapentinoid abuse
- Plan for inpatient hospitalization either leading up to or after treatment
- Pregnancy
- Inability of the patient to consent for themselves in English
- Allergy to gabapentinoid
- Liver failure or hepatic dysfunction
- No email address that is regularly checked

### **OVERVIEW OF STUDY DESIGNATION**

Design

This is a randomized, controlled clinical trial on the use of perioperative pregabalin in order to decrease ureteral stent related symptoms and decrease opioid usage after ureteroscopy with stent placement. Patients undergoing ureteroscopy with stent placement will receive a single dose of 300 mg pregabalin PO or an identical appearing placebo in the preoperative area.

#### Pre-op standardized care

After obtaining electronic written informed consent, patients will be enrolled.

Subsequently, all patients will be given a single dose of pregabalin 300 mg PO or an identical appearing placebo with a sip of water approximately one hour before surgery. This will be administered per standard intuitional practice. It will not be recorded in the regular medical chart of the patient.

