#### Post-op standardized care

Perioperative care, surgery, and anesthesia for all subjects will be per standard hospital protocol.

To qualify for discharge from the PACU, per standard protocol, all patients will have had to have ambulated, voided, tolerated PO intake, and have pain subjectively adequately controlled.

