#### THERAPEUTIC AND DIAGNOSTIC AGENTS

Pregabalin is an oral agent approved for use in fibromyalgia and neuropathic pain. A single dose of compounded 300mg PO will be given to all patients.

A standard inactive placebo will be used.

The medications will be compounded so as to have identical appearance. This will be performed by the investigational pharmacy at the University of Missouri.

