#### BIOSTATISTICS

#### Sample Size

The study will be powered with an 80% probability to detect a 10% difference in the primary outcomes. It will also assume a loss to follow up rate of 50%. This will require approximately 200 total subjects with a planned 1:1 placebo to active treatment enrollment ratio. We estimate at least 500 eligible procedures are conducted each year at our institution. Accounting for excluded patients and those who do not wish to participate, we estimate that full enrollment should be attainable within one year.

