#### Participant randomization

Randomization will be undertaken using the randomization module available in REDCap. Patients will be randomized to either "Group A" or "Group B". Medications will be distributed via the investigational pharmacy according to patient allotment. No one outside the investigational pharmacy will have knowledge of which group receives active medication.

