#### **PROTECTION OF HUMAN SUBJECTS**

#### Benefits and Risks

The experimental intervention (perioperative pregabalin administration) is currently used at University of Missouri Hospital through the ERAS protocol. Numerous studies have shown significant patient benefits in all fields, including Urology. Several reviews have demonstrated the efficacy and safety of perioperative

gabapentinoid administration. The principal side effects of pregabalin are temporary cognition/coordination changes, with a very low risk of serious side effects. Therefore, we do not believe that the therapeutic aspects of this trial pose any serious risk different from patients undergoing ureteroscopy with stent placement under standard procedures.

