#### Toxicities and side effects

Adverse outcomes are not anticipated with the regimen of pregabalin used in this study. Patients are closely monitored during the perioperative period and any serious events will be immediately brought to the attention of the study staff. All potential side effects will be recorded in questionnaires.

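### The study dose is kept out of the regular chart, so a clinician relying on its medication record would not see that pregabalin 300 mg may have been given

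*Protocol*

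**What the plan says.** Under Pre-op standardized care, each enrolled patient takes a single oral dose of pregabalin 300 mg or a look-alike placebo about one hour before surgery. The section then states: "It will not be recorded in the regular medical chart of the patient".

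The sections that bear on this rule are:

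- **Surrounding care (Post-op standardized care).** "Perioperative care, surgery, and anesthesia for all subjects will be per standard hospital protocol".
- **Use of the drug at the site (Benefits and Risks).** Pregabalin given around surgery "is currently used at University of Missouri Hospital through the ERAS protocol".
- **Who is excluded (Subject Exclusion list).** The gabapentinoid criteria are "Chronic gabapentinoid use", a history of abuse, and allergy. A one-off perioperative dose is not mentioned.
- **Safety reporting (Toxicities and side effects, under Protection of Human Subjects).** The plan relies on close monitoring, and "any serious events will be immediately brought to the attention of the study staff".
- **Blinding.** "The medications will be compounded so as to have identical appearance" (Therapeutic and Diagnostic Agents), and "No one outside the investigational pharmacy will have knowledge of which group receives active medication" (Participant randomization).

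**The concern.** The medication record is the usual place for a treating clinician to check what a patient has been given. Here it omits a centrally acting drug at 300 mg, given shortly before general anesthesia. Two consequences follow for someone who relies on that record.

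The first is attribution. The Protocol names short-lived effects on thinking and coordination as the main side effects of pregabalin (Background; Benefits and Risks). A clinician who meets such changes and looks at the medication record finds nothing there pointing to pregabalin. Routing serious events to study staff works best when the clinician knows that a study drug is in play.

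The second is prescribing. A clinician thinking of giving a gabapentinoid would not learn from the medication record that the patient may already have had one.

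What is at stake is safety information during the conduct of the trial. The primary comparison is not affected.

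**Working it through.** The plan states no figure on this point, so there is none to reproduce. The check is a comparison of sections plus one division.

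**1. Is the dose visible anywhere else?**

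| Section | What it provides | Does it put the dose before a clinician reading the chart? |
|---|---|---|
| Pre-op standardized care | The dose is given and, by rule, not charted | No |
| Post-op standardized care | Standard hospital care and discharge criteria | No alert or notice described |
| Usual care | Lists PACU and discharge medication as routinely documented | No; the preoperative study dose is not in the list |
| Not part of usual care (table) | Study staff complete a PACU form; the patient repeats the clock drawing test and pain scale | No; these are study questionnaires |
| Criteria for Therapeutic Response | Optional PACU questionnaire for nurses | No; it is not described as a dose record |
| Toxicities and side effects; SAE Reporting | Serious events go to study staff and the IRB | No; this acts after an event |
| Recruitment Plan | Urology physicians introduce the study | No, though those physicians may know who enrolled |

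No section supplies a substitute for the missing entry. The post-operative instructions and the consent form are separate files that cannot be seen here, and may tell the patient about the drug.

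**2. How many patients?**

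Input: "approximately 200 total subjects with a planned 1:1 placebo to active treatment enrollment ratio" (Protocol, Sample Size; the SAP's Power Analysis gives the same total and ratio).

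Uncharted active doses = total × active share = 200 × 1/2 = 100. The other 100 or so would have an uncharted placebo.

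This assumes that enrolled patients receive their dose. Loss to follow-up after surgery does not reduce the count; withdrawal before dosing would.

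**3. Does the blind need the rule?**

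The two products look the same, each patient gets exactly one dose, and only the investigational pharmacy holds the key. Suppose every chart carries the same line. A reader of that line knows only that the chance of active drug is 1/2, which the 1:1 ratio already tells anyone familiar with the trial. The line therefore carries no information about the arm.

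The group letter is different. Patients are assigned to Group A or Group B, so if letters were charted, learning one patient's treatment would reveal everyone's. The letter should stay out of the chart.

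**The case against.** The strongest reply is that the gap is narrow. The drug acts on the day of surgery, and that is when the trial is watching: study staff complete a PACU form, the patient repeats the clock drawing test, and that test is the plan's own measure of neurological change. Urology physicians introduce the study and patients consent to it, so some of the care team will know who is enrolled. The documents also do not say whether the regular chart shows enrolment or the signed consent; if it does, a clinician who reads beyond the medication record would have a lead. All of this stands. It limits the point to clinicians who depend on the medication record, mainly those outside the study team or seeing the patient later. It does not show that the rule serves a purpose.

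A reader might go further and infer that trial patients will be dosed twice, because pregabalin is in use at the hospital and no section expressly bars another dose. The documents do not support that. They do not say that the ERAS protocol covers ureteroscopy, and they give no rate of non-study dosing, which may be zero. The section on alternatives to participation says that a patient outside the trial might or might not be given pregabalin, with the rest of care the same. That shows routine pregabalin is possible in this procedure, but it can equally be read as the study dose taking the place of the surgeon's choice. Any count of duplicate doses would be an assumed rate multiplied by 100, so none is offered.

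One could also read the sentence as meaning only that the treatment arm is not charted. It does not say that, and the change proposed below would settle it.

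**Conclusion.** The point holds as a minor safety and conduct matter. The Protocol keeps the dose out of the regular chart and describes no blinded entry or alert in its place. About 100 of roughly 200 patients would have an active 300 mg dose that the medication record does not show.

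The conclusion rests on the planned enrolment and ratio, and on the absence of a substitute in the text that can be seen. It does not assume that anyone is harmed: the Protocol describes the risk of serious side effects as very low, and the 100 counts missing entries. Nor do the documents show that treating staff are unaware of enrolment, that side effects in the PACU would be missed, or that the blind or the analysis is weakened. What is left is a rule that withholds useful information from some clinicians and that the blind does not need.

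**What to change.** In Pre-op standardized care, replace the sentence that keeps the dose out of the chart with: *The dose is charted for every patient as study drug: pregabalin 300 mg or placebo (blinded).* Leave out the Group A/B letter. Set the entry up so that it is not billed to the patient, in keeping with Financial Costs and Burdens.

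The cost is one uniform chart entry per patient and one changed sentence. The documents give no price for this; that it is small is a judgement. The blind, sample size, visits, questionnaires and analysis stay as they are.

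The entry has a limit: it tells a clinician that pregabalin is possible, not that it was given. It does not replace an emergency unblinding procedure, which the visible text does not describe.

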#### Post-op standardized care

Perioperative care, surgery, and anesthesia for all subjects will be per standard hospital protocol.

To qualify for discharge from the PACU, per standard protocol, all patients will have had to have ambulated, voided, tolerated PO intake, and have pain subjectively adequately controlled.

#### THERAPEUTIC AND DIAGNOSTIC AGENTS

Pregabalin is an oral agent approved for use in fibromyalgia and neuropathic pain. A single dose of compounded 300mg PO will be given to all patients.

A standard inactive placebo will be used.

The medications will be compounded so as to have identical appearance. This will be performed by the investigational pharmacy at the University of Missouri.

#### **RECRUITMENT PLAN**

Patients will be recruited from the Division of Urology, Department of Surgery. The study will be introduced to every eligible patient scheduled for ureteroscopy with stent placement by the participating consenting physicians from the Department of Surgery-Urology Division and an electronic consent obtained prior to surgery by the consenting research personnel. Candidate subjects will be provided time to consider the study, to read the informed consent document at their convenience, and discuss the study with family and others, as desired. It will be clearly indicated that non-enrollment in the study will not negatively affect the patient's care.

## PRETREATMENT EVALUATION

This study does not require any additional pretreatment evaluations other than those which are part of current clinical care standards for a patient undergoing ureteroscopy with stent placement at University of Missouri. Preoperative evaluations typically include the following:

- Routine history and physical examination to include documentation of any comorbidities, medications (including complementary and alternative medications), family history, social history (alcohol and tobacco usage), height, body weight
- Past medical history including previous treatment for addiction

- Past surgical history including other uses of stents in the patient's lifetime
- Evaluation of renal function
- Any woman of child bearing age who believes she may be pregnant receives a pregnancy test

#### SURGICAL PLAN

The technique of surgery will have been determined to be ureteroscopy with stent placement based on the discretion of the surgeon and patient. None of the techniques utilized in the study are considered experimental and all are considered standard therapeutic options for patients with indications for this procedure. Typical indications include nephroureterolithiasis and evaluation for malignancy.

The operating team will consist of surgeons at University of Missouri Department of Surgery-Urology Division. The procedures are performed under standardized general anesthesia with standard intraoperative vital sign monitoring.

### **EVALUATION DURING TREATMENT/INTERVENTION**

#### Not part of usual care

This protocol requires several evaluations outside those typically used. These are all questionnaires.

Timing	Questionnaire	Respondent
Before day of surgery OR on day of surgery	Screening questionnaire	Study staff
	Baseline questionnaire and demographic information	Patient
	E-consent	Patient
	Preop Watson clock drawing test and visual analog scale of pain	Patient
Day of surgery	PACU	Study staff
	Watson clock drawing test and visual analog scale of pain \$	Patient
3 days post op	Early patient questionnaire	Patient
7 days post op	Early patient questionnaire	Patient
30 days post op	30 days post op chart review	Study staff
	Early patient questionnaire \$	Patient
90 days post op	Late patient questionnaire	Patient
6 months post op	Late patient questionnaire	Patient
1-year post op	Late patient questionnaire	Patient
	1-year post op chart review	Study staff
Untimed	Unanticipated contact	Study staff/Treatment staff
	Evaluation of trial	Patient

\$ indicates questionnaires for which compensation will be provided. Please see details of compensation.

#### Usual care

Routine evaluation and management for those undergoing ureteroscopy with stent placement include: ASA classification, assigned by the anesthesiologist Deep venous thrombosis prophylaxis per standardized pathway Estimated blood loss Use of intraoperative fluids (crystalloid, colloid, blood products) PACU medication Discharge medication Follow up plan

#### **TOXICITIES/SIDE EFFECTS**

Various symptoms have been associated with the administration of pregabalin in the perioperative setting. The risk of serious adverse events in this use of pregabalin is low [27] and the potential benefits of this treatment may outweigh the risks. This will be recorded in the PACU questionnaire.

Surgical complications will be assessed prospectively and retrospectively and reviewed using the institutional standard for complications reporting for all surgical patients as followed by the Department of Surgery. Standardized graded complications and adverse effects at UM utilize the five-point modified Clavien-Dindo system. Grade I include complications requiring monitoring but no intervention; Grade II requires bedside or medical treatment; Grade III constitute adverse events requiring surgical or procedural intervention with return to normal functioning; Grade IV includes disabling, life-threatening complications with resulting functional loss and grade V is death of the patient. This is a modification of the Clavien-Dindo system for reporting complications with defined, categorized and classified events that will be segregated into time periods of ≤30 days, 31-90 days and > 90 days after surgery and includes medication complications following NCI CTCAE version 5 guidelines.

### **CRITERIA FOR THERAPEUTIC RESPONSE/OUTCOME ASSESSMENT**

The intraoperative period is defined as the period from anesthesia induction to the extubation of the trachea. The surgical time is determined from the incision to the final skin closure.

The postoperative period is defined as the period from the extubation to various study endpoints.

Blood loss is defined as the estimate accounted from the suction device and absorptive sponges during the procedure, as described and agreed upon by the surgeon, anesthesiologist, circulating nurse, and surgical technician as covered by institutional guidelines.

The patient's pain will be evaluated with a visual analogue scale of pain [28]. This may either be done digitally or by paper [29].

Adverse events will be measured with an optional PACU questionnaire for nurses as well as by monitoring of unanticipated contact.

Neurological changes will be measured using the Watson[30] clock drawing test.

Satisfaction will be evaluated via questionnaires at subsequent time points.

Need for opioid pain medication will be carefully tracked via patient questionnaire, chart review, and review of any available prescription database.

#### **CRITERIA FOR REMOVAL FROM STUDY**

Patients will be withdrawn from the study if they express a desire to do so or if it is determined to be in the patient's best interest to do so.

#### BIOSTATISTICS

#### Sample Size

The study will be powered with an 80% probability to detect a 10% difference in the primary outcomes. It will also assume a loss to follow up rate of 50%. This will require approximately 200 total subjects with a planned 1:1 placebo to active treatment enrollment ratio. We estimate at least 500 eligible procedures are conducted each year at our institution. Accounting for excluded patients and those who do not wish to participate, we estimate that full enrollment should be attainable within one year.

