#### Primary Endpoints

The primary endpoint will be the value on the visual analog scale of pain score supplied by the patient approximately one hour after reaching the post-operative area.

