#### Patient incentives

The patients will be offered the following compensation:

Timing	Amount	Requirement
Day of surgery	\$5.00	Completion of day of surgery
		clock drawing test and visual
		analog scale
30 days post-op	\$5.00	Completion of early patient
		questionnaire

We may extend this to later time points pending future funding.

Monies will be supplied to patients in the form of e-gift certificates.

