Group sample sizes of 59 per group achieve 80% power to reject the null hypothesis of equal means when the population mean difference in VAS score is as little as 1 unit, assuming the standard deviations of 1 for group 1 (based on our pilot study) and 2.5 for group 2 (from literature), and with a significance level (alpha) of 0.05 using a two-sided two-sample unequal-variance t-test. Assumption about 40% dropout rate, it requires approximately 200 total subjects with a planned 1:1 placebo to active treatment enrollment ratio. We estimate at least 500 eligible procedures are conducted each year at our institution. Accounting for excluded patients and those who do not wish to participate, we estimate that full enrollment should be attainable within one year.

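### Protocol and SAP both claim 80% power from about 200 subjects, but at 50% and 40% loss; the only derivation given supports 200 up to 41% loss and yields about 73% power at 50%

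*Protocol*

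**What the plan says.** The protocol (Biostatistics, Sample Size) sets the target: "The study will be powered with an 80% probability to detect a 10% difference in the primary outcomes". It continues: "It will also assume a loss to follow up rate of 50%. This will require approximately 200 total subjects", randomized 1:1. It gives no standard deviation, significance level, test or evaluable number per group.

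The SAP (Power Analysis) gives the inputs: "Group sample sizes of 59 per group achieve 80% power to reject the null hypothesis of equal means". These are a mean VAS difference of 1 unit, SDs of 1 (pilot) and 2.5 (literature), and a two-sided unequal-variance t-test at 0.05. It then inflates for loss: "Assumption about 40% dropout rate, it requires approximately 200 total subjects", also 1:1.

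Neither document explains why the loss rates differ or says which outcome the rate describes. The protocol's Primary Endpoints section defines the primary outcome as a VAS pain score "supplied by the patient approximately one hour after reaching the post-operative area". Its Patient incentives table pays participants for "Completion of day of surgery" assessments, the VAS among them.

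**The concern.** A fixed evaluable number, inflated for two different loss rates, cannot give the same enrolment total. If 118 evaluable participants are needed, 40% and 50% loss lead to totals that differ by about 40. Both documents nevertheless arrive at about 200 with 80% power, so at least one statement does not follow from its own loss rate unless the protocol rests on inputs it does not report.

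What is at stake is whether the sample-size justification can be relied on. A reader with both documents cannot tell which loss rate the trial was planned for, or whether that rate concerns the day-of-surgery VAS or the later questionnaires. If the protocol's 50% is taken at face value for the primary outcome, its 80% is overstated under the only derivation available.

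**Working it through.** **Inputs.** From the SAP: difference 1 unit; SDs 1 and 2.5; two-sided alpha 0.05; unequal-variance (Welch) t-test; 59 per group; 40% dropout. From the protocol: 50% loss. From both: 80% power, about 200 enrolled, 1:1.

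**Assumption.** The protocol's difference of 10% is read as 1 unit on a 0–10 VAS. The documents do not state the scale's range.

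**Formulas.** With n evaluable per group:
- noncentrality = 1 / √((1² + 2.5²)/n) = √(n/7.25)
- Satterthwaite df = 7.25² × (n − 1) / (1² + 6.25²) = 52.5625 × (n − 1) / 40.0625
- power from the noncentral t at the two-sided 5% critical value
- enrolment = evaluable total / (1 − loss)

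**Step 1: reproduce the SAP.** At n = 59, noncentrality is √(59/7.25) = 2.85, df is 76.1 and power is 80.4%. At n = 58 power is 79.7%. So 59 is the smallest group size that reaches 80%, as the SAP says. Inflating, 118/(1 − 0.40) = 197, which agrees with about 200.

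**Step 2: apply the protocol's loss rate.** 118/(1 − 0.50) = 236, which is not about 200. In the other direction, 200 × 0.50 leaves 100 evaluable, or 50 per group. Noncentrality is then √(50/7.25) = 2.63, df is 64.3 and power is 73.5%. Simulation with 100,000 replicates gave 73.7%. The difference detectable with 80% power at 50 per group is 1.08 units.

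**Step 3: find the break-even.** Two hundred enrolled still yields 118 evaluable up to a loss of 1 − 118/200 = 41%.

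**Step 4: try other routes to 200 at 50% loss.** The normal approximation gives 57 per group, hence 114/0.5 = 228. Inflating by multiplication gives 118 × 1.5 = 177. Neither is close to 200.

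**Step 5: power with 200 enrolled, across loss of the PACU VAS.** The documents give no expected loss for this measurement, so a range is shown.

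| Loss | Evaluable per group | Power |
|---|---|---|
| 0% | 100 | 95.8% |
| 10% | 90 | 93.8% |
| 20% | 80 | 90.8% |
| 30% | 70 | 86.7% |
| 40% | 60 | 81.1% |
| 41% | 59 | 80.4% |
| 50% | 50 | 73.5% |

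**The case against.** The best defence is that the protocol's paragraph contains no arithmetic to be wrong. It states no SD, alpha or evaluable number, so the 73% comes from placing the SAP's inputs behind the protocol's sentence. With a common SD of about 1.78 (normal approximation), 50 per group would give 80% power; a one-sided 5% test with the SAP's SDs would give 83%. The protocol may even have had another outcome in mind. It refers to primary outcomes in the plural and to loss to follow-up, and its Analysis section, having named the PACU VAS as primary, describes the primary t-test as a comparison of opioid prescribed. The protocol also defers to a formal SAP, and that SAP has a complete calculation at 40%. Finally, a score taken about an hour after arrival in recovery should seldom be missing.

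Part of this stands. The 73% is conditional on the SAP's inputs, and the practical consequence is probably small. The rest does not remove the problem. Neither document states an SD near 1.78, and the SAP specifies a two-sided test. The protocol's Primary Endpoints and Analysis sections and the SAP all name the VAS as primary. The deferral to the SAP concerns the analysis and does not say that the protocol's sample-size assumptions are replaced. The clash between 40% and 50% at one total and one power needs no borrowed input.

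**Conclusion.** The concern holds. The SAP's calculation is sound: 59 per group reproduces and 40% dropout leads to about 200. The protocol's combination of 50% loss, about 200 subjects and 80% power does not follow from the only derivation in the documents. At that loss rate the derivation gives 73.5% power, 6.5 points below the stated figure, or would need 236 enrolled.

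This rests on the SAP's difference, SDs, alpha and test also applying to the protocol's statement, and on 10% meaning 1 unit of a 0–10 scale. It is a finding about planned power and about consistency between the documents. It does not show that the trial will be underpowered: on the SAP's inputs, 200 enrolled gives more than 90% power if no more than 20% of the PACU scores are lost. The statement should be corrected, but it threatens neither the design nor the analysis.

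**What to change.** State one loss rate in both documents and say that it applies to the PACU VAS, because that is the outcome whose 59 per group the SAP inflates. There are two consistent ways to do this with 200 enrolled:

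- change the protocol's rate to 40% and keep 80% power; or
- keep 50%, bring the SAP into line, and restate planned power as about 73% for a 1-unit difference.

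In the protocol's Sample Size paragraph, replace the 10% wording with the SAP's inputs: a 1-unit VAS difference with the scale's range, SDs 1 and 2.5, two-sided alpha 0.05, unequal-variance t-test. If the 40% or 50% was meant for the later questionnaires, say so and give the expected loss for the PACU VAS separately; the table above shows the power that follows.

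The cost is one or two sentences. Enrolment, endpoint and analysis are unchanged. If 50% is kept for the primary outcome, the sponsor has to accept a less favourable stated power.
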